#### C. Study Design and Research Methods

This study is an open label, cross-over study, evaluating the plasma and peritoneal fluid pharmacokinetics of dalbavancin after either intravenous or intraperitoneal administration. The

patients will be randomly assigned to receive dalbavancin either intravenously or intraperitoneally on study visit 1. The patients will receive the alternate administration technique following the washout period at visit 4. Patients will be administered dalbavancin either intravenously or intraperitoneally on study day 0. Pharmacokinetic analysis will be conducted on days 0, 7, and 14. Following the wash out period of 45 days or greater, the same 10 patients will cross-over and then be administered dalbavancin via the alternate administration technique received in visit 1 on study day 0. Pharmacokinetic analysis will be conducted again on days 0, 7, and 14. (see Appendix 1)

*Sample Size:*

Ten (n=10) patients will be evaluated in this pharmacokinetic evaluation. Since this is a descriptive pharmacokinetic study a sample size calculation was not performed

*Plasma and peritoneal fluid sampling:*

Dalbavancin will be administered on study day 0. On the intravenous administration day dalbavancin will be administered as a 30-minute IV infusion. On the intraperitoneal administration day, dalbavancin will be administered in the peritoneal dialysis fluid with a 6 hour dwell time. On day 0, patients will undergo plasma and peritoneal fluid pharmacokinetic sampling for determination of dalbavancin concentrations at time zero, 1 hour, 2 hours, 3 hours, 4 hours, 6 hours, at time of volume exchange. Patients will be given a specimen collection cup and asked to collect ~30 ml of peritoneal dialysate following scheduled nocturnal dwell approximately 24 hours following the administration of dalbavancin administration. Patients will report for a single PK measurement on study days 7 and 14. (18 total plasma and 18 total peritoneal fluid samples per patient). Blood samples will be drawn from a peripherally inserted intravenous catheter. Peritoneal fluid samples will be drawn from the already placed peritoneal dialysis catheter. Blood samples will be immediately centrifuged at 3000g and plasma and peritoneal fluid samples will be stored at -80°C until analysis.

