##### *Pharmacokinetic analysis:*

Plasma and peritoneal fluid concentration-time data for dalbavancin will be evaluated using a multi-compartment model in Phoenix WinNonlin (Pharsight corporation). One, two, and three compartment models will be explored. The following PK parameters will be calculated for plasma and dialysate samples: Cmax – measured, Tmax – measured, Cmin – measured. Fraction of intraperitoneal (IP) dose absorbed [(Dose – drug concentration remaining in dialysate at end of

antibiotic dwell)/Dose].  $K_{el}$  – elimination rate constant.  $T_{1/2} = 0.693/K_{el}$ .  $K_{pc0-6}$  – rate constant for distribution of dalbavancin from peritoneal cavity between 0-6 hours. Distribution half-life in the peritoneal cavity between 0-6 hours ( $t_{1/2} = \ln 2/k_{pc0-6}$ ). Clearance systemic =  $(F \times \text{Dose})/AUC_{0-\infty}$ . Clearance peritoneal – dalbavancin concentration in spent dialysate/AUC of peritoneal fluid. Non-dialysis clearance –  $Cl = Cl_{plasma} - Cl_{peritoneal}$ .  $AUC_{0-\infty}$  – linear trapezoidal method.  $AUC_{0-12}$  hours – linear trapezoidal method. Volume of distribution for each compartment –  $Cl/k_{el}$ ; nonsteady state equations will be utilized. The ratio of plasma dalbavancin to dialysate plasma concentration at each time point –  $C_{plasma}/C_{dialysate}$  and via  $AUC_{plasma}/AUC_{dialysate}$ . Given the sample size of 10 patients completing each treatment modality we will be able to calculate means and standard deviations for all included pharmacokinetic parameters. We will incorporate the dalbavancin PK parameters into a nonlinear mixed effects model (NONMEM) or ADAPT II to determine the pharmacokinetics and examine the effects of varying dosing strategies on plasma and peritoneal fluid concentrations.

*Analysis of pharmacodynamic targets:*

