Pharmacodynamic parameters will be evaluated in order to determine whether dalbavancin dosing results in initial and steady-state plasma and peritoneal concentrations that are adequate for treatment of infections due to common pathogens (Staph aureus, Coag neg staph, and enterococcus). Monte Carlo simulation (Crystal Ball version 7, Decisioneering, Inc., Denver, CO) will be used in this study to calculate probability of target attainment (PTA) for pharmacodynamic goals. The model randomly applies values for  $C_{max}$  and  $AUC_{0-12}$  derived from data obtained from the study patients. We will utilize CLSI and EUCAST MIC data for the common gram positive pathogens. We will place these MIC distributions into our Monte Carlo simulation for comparison to dalbavancin plasma concentrations and PK variability. From these studies, MIC frequency distributions will be constructed and used in the Monte Carlo simulations. Ten thousand simulations will be performed at each MIC value and for each of the selected pathogens.

[figure not shown]
[figure not shown]
*Statistical comparisons of PK/PD findings*

Intra-patient pharmacokinetics and pharmacodynamics of dalbavancin will be compared between intravenous and intraperitoneal administration using the paired-t test. Given the sample size of 10 patients completing each phase of the study, we will be able to detect a mean difference in area under the curve between the two treatment modalities of 1527 mg·hr/L at a power of 80%. Probability of target attainment will be compared with the paired t-test. Statistical comparisons will be compared using SAS version 9.3. A p-value < 0.05 will be considered significant.

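### Measured Tmax falls under a blanket mean/SD summary and paired t-test; one maximum at day 7 or 14 among 10 patients could distort both, and a median with a rank-based test costs nothing

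*Combined protocol and SAP*

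**What the plan says.** Section IV.F, under pharmacokinetic analysis, introduces its list with "The following PK parameters will be calculated for plasma and dialysate samples" and includes "T max – measured". Tmax is therefore an observed sampling time in both fluids, not a model estimate. The same paragraph says of the 10 patients that "we will be able to calculate means and standard deviations for all included pharmacokinetic parameters". Under statistical comparisons, the plan states: "Intra-patient pharmacokinetics and pharmacodynamics of dalbavancin will be compared between intravenous and intraperitoneal administration using the paired-t test", with p < 0.05 as the criterion. Tmax is neither named nor excepted there.

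Section IV.C fixes the possible values. Day 0 samples are taken "at time zero, 1 hour, 2 hours, 3 hours, 4 hours, 6 hours, at time of volume exchange". For dialysate only, patients also "collect ~30 ml of peritoneal dialysate following scheduled nocturnal dwell approximately 24 hours following the administration". After that, "Patients will report for a single PK measurement on study days 7 and 14".

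**The concern.** Tmax read off a sampling schedule is a coarse, discrete variable. Here the schedule has a very wide gap: plasma has nothing between the day 0 volume exchange and day 7, and dialysate has only the sample at about 24 h. A patient whose highest value falls on the far side of the gap contributes 168 h or 336 h, while the others contribute a few hours. With 10 pairs, such a value inflates both the mean and the SD of the differences, so the t statistic can shrink as the difference grows. At stake are an unrepresentative Tmax in the results table and a route comparison that may miss a consistent within-patient difference.

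**Working it through.** **Plan's own figure.** The documents give none for Tmax. The only power statement (1527 mg·hr/L at 80% power) concerns AUC and has no bearing here.

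**Inputs from the documents.** Ten pairs; post-dose times of 1, 2, 3, 4 and 6 h, volume exchange (no fixed clock time), about 24 h (dialysate only), 168 h and 336 h; significance at 0.05, taken as two-sided because the plan does not say.

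**Assumed values.** The documents contain no Tmax data, so the sets below are illustrations on the scheduled times. IP dialysate Tmax is taken as 1 h in all 10 patients, on the view that dosed fluid declines from the first sample.

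**Formulas.** t = mean difference / (SD of differences / √10), with 9 degrees of freedom. When all 10 differences share a sign, the exact signed-rank p is 2/2^10 = 0.00195, and so is the sign-test p.

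| IV dialysate Tmax | Mean (h) | SD (h) | Median (h) | Mean difference (h) | t | t-test p |
|---|---|---|---|---|---|---|
| 9 at 6 h, 1 at 168 h | 22.2 | 51.2 | 6 | 21.2 | 1.31 | 0.22 |
| 8 at 6 h, 2 at 168 h | 38.4 | 68.3 | 6 | 37.4 | 1.73 | 0.12 |
| 5 at 6 h, 4 at 24 h, 1 at 168 h | 29.4 | 49.5 | 15 | 28.4 | 1.81 | 0.10 |
| 9 at 24 h, 1 at 168 h | 38.4 | 45.5 | 24 | 37.4 | 2.60 | 0.03 |
| 9 at 6 h, 1 at 24 h | 7.8 | 5.7 | 6 | 6.8 | 3.78 | 0.004 |
| 5 at 6 h, 5 at 24 h | 15.0 | 9.5 | 15 | 14.0 | 4.67 | 0.001 |

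The exact signed-rank p is 0.002 in every row.

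First row in full: mean = (9×6 + 168)/10 = 22.2. Sum of squares = 9×16.2² + 145.8² = 23,619.6, so SD = √(23,619.6/9) = 51.2. Mean difference = 22.2 − 1 = 21.2, and t = 21.2/(51.2/√10) = 1.31.

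**General form.** With nine patients at a hours, one at L hours, and 1 h in all by the other route, the algebra reduces to t = 1 + 10(a − 1)/(L − a). As L grows, t falls towards 1 and p rises to 0.34. The critical value with 9 degrees of freedom is 2.262. For L = 168, significance is lost when 10(a − 1) < 1.262(168 − a), that is, a below about 19.7 h. So nine at 6 h lose it and nine at 24 h keep it, as in the table.

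**Plasma illustration, also assumed.** Take IV Tmax as 1 h in eight patients and 2 h in two, and IP Tmax as 4 h in two and 6 h in eight.
- No late maximum: IP mean 5.6 h, SD 0.8 h, t-test p < 0.0001.
- One IP maximum moved to 168 h: mean 21.8 h, SD 51.4 h, p = 0.23.
- One moved to 336 h: mean 38.6 h, SD 104.5 h, p = 0.29.
- In all three, the IP median is 6 h and the exact signed-rank p is 0.002.

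**Late maximum in the opposite direction.** If one IV plasma value is 168 h instead, the mean difference becomes −12.3 h (t-test p = 0.48), although nine of 10 patients peak later by the IP route. The signed-rank p is then 0.088, and the sign-test p is 2×(1 + 10)/2^10 = 0.021.

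**The case against.** - **The plan's commitment is loose.** The sentence on means and SDs reads partly as a remark on what 10 patients allow, and does not rule out medians. The t-test sentence names no parameter, and the only one given a detectable difference is AUC. This stands as a limit: applying the t-test to Tmax follows from general wording. But no other summary or test is planned.
- **The harm is conditional.** A reader might infer that one late maximum will decide the mean, SD and p-value. The documents do not support that. They give a half-life of about 8.5 days, so elimination alone leaves 2^(−7/8.5) ≈ 57% at day 7 and 2^(−14/8.5) ≈ 32% at day 14, which argues against a late plasma peak. For dialysate, no dwell length is fixed before the day 7 and 14 samples, so a late maximum cannot be excluded, but its likelihood is unknown. Sets without a 168 h value stay significant, as does nine at 24 h with one at 168 h.
- **Wrong for both fluids?** A reader might also infer that the reported Tmax would be wrong in plasma and dialysate alike. That goes too far. After a 30-minute infusion with the first post-dose sample at 1 h, IV plasma Tmax is expected to be about 1 h in nearly everyone. Mean and median then agree, and the summary is correct though uninformative. A mean of skewed values is unrepresentative, not a false number.
- **Little depends on Tmax.** Target attainment uses Cmax and AUC0-12, and the study calls itself descriptive. This stands and limits the weight of the point.
- **The signed-rank test has its own limits.** As a test of a median shift it assumes symmetric differences, and ties will be common. This also stands, and is why the sign test is offered as an alternative.

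**Conclusion.** The point holds as a minor one. Mean, SD and paired t-test fit poorly a discrete time whose possible values jump from hours to 168 h. If one or two of 10 patients have a day 7 or day 14 maximum while most of the rest peak within about 6 h, the mean is pulled several-fold above the median, and the t-test can fall short of significance (p = 0.12 to 0.29 in the illustrations with every other value at 6 h or below) although all 10 differences share a sign. This rests on assumed Tmax values, a two-sided test, and reading the general t-test sentence as covering Tmax. Nothing in the documents shows that late maxima will occur, and no target or dosing conclusion depends on Tmax.

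**What to change.** Add to section IV.F, under pharmacokinetic analysis and statistical comparisons, wording such as:

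*Tmax is exempt from the mean/SD summary and the paired t-test. It will be reported as median and range, with counts by scheduled sampling time, for each route and fluid. Any comparison between routes will use an exact paired rank-based test (exact signed-rank, or the sign test where ties and skew are marked). IV plasma Tmax is largely set by the first post-dose sampling time and will be interpreted accordingly.*

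The choice between the two tests should be settled before the data are seen. The change needs no new data, visits or patients. It does not remove the gap before day 7, so a maximum recorded there will still be poorly located in time.

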### **I. Hypotheses and Specific Aims:**

#### Hypothesis:

Dalbavancin maintains adequate plasma and peritoneal fluid concentrations for 2 weeks after a single 1500 mg dose when administered intravenously or intraperitoneally, making it a viable and convenient option for treating peritoneal dialysis patients with peritonitis

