**Washout:** During the 45 day or greater washout portion of this study the patients will not be asked to come in for any visits. This timeframe, which is greater than 5 half-lives of dalbavancin, is to ensure that all of the medication (dalbavancin) has left the patients' system before administering another dose of the medication.

**Laboratory tests:** The laboratory tests to be performed as part of this study include pregnancy testing to confirm eligibility and comprehensive metabolic panels if one is not documented within 30 days prior to the initiation of protocol to determine Child-Pugh score. These will be done at an initial screening visit if required to coincide with clinic appointment before visit 1.

**Pharmacokinetic Assessments:** 4 mL of blood will be collected in a purple top (EDTA) tube and 4 mL of peritoneal fluid in a urine collection cup at pre-dose, and 1, 2, 3, 4, 6, dialysis volume exchange. Blood and peritoneal fluid will be placed in an ice bath to chill until centrifuged. Plasma will be harvested within 30 minutes of each blood sample and will be stored at -80°C until assaying.

**Sample Coding and Storage:** Study samples will be coded with an indirect identifier and stored in [name] access-controlled laboratory.

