#### Risk of development of drug-resistant bacteria

Receiving dalbavancin in the absence of a proven or strongly suspected bacterial infection increases the risk of the development of drug-resistant bacteria. Currently there are no reported cases of dalbavancin resistance reported within the literature. Dalbavancin also shows extremely high potency against medically important *Staphylococcal* and *Streptococcal* species, including methicillin resistant *Staphylococcus aureus*. To date in vitro dalbavancin resistance has not been induced but possible mutations have increased the minimum inhibitory concentration. This has not been seen clinically, and we will maximize the minimum inhibitory concentration to area under the curve ratio, utilizing the 1500 mg dosing strategy.

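### The hypothesis concerns the two weeks after a single dose, but adequacy is to be judged at initial and steady-state concentrations; day 14 is sampled and never named as the point of judgement

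*Combined protocol and SAP*

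**What the plan says.** Section I (Hypothesis) states: "Dalbavancin maintains adequate plasma and peritoneal fluid concentrations for 2 weeks after a single 1500 mg dose", by either the intravenous or the intraperitoneal route.

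Section IV.F (Analysis of pharmacodynamic targets) is the only place that describes how adequacy will be judged. It sets out to determine whether "dalbavancin dosing results in initial and steady-state plasma and peritoneal concentrations that are adequate for treatment of infections due to common pathogens". The tool is a Monte Carlo simulation to "calculate probability of target attainment (PTA) for pharmacodynamic goals". Its pharmacokinetic inputs are Cmax and AUC0-12, "derived from data obtained from the study patients". MIC distributions come from CLSI and EUCAST, and plasma is the only fluid named in the comparison with them. On output the text says: "Ten thousand simulations will be performed at each MIC value and for each of the selected pathogens". Two figures next to this text are not shown in the copy reviewed.

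Section IV.C gives one dose on day 0 of each period and takes plasma and peritoneal fluid on days 0, 7 and 14. Section IV.D (Washout) says the gap of at least 45 days "is to ensure that all of the medication (dalbavancin) has left the patients' system before administering another dose of the medication".

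The only pre-set test is a paired t-test of intravenous against intraperitoneal administration, applied to the PK/PD results and to target attainment, with the rule "A p-value < 0.05 will be considered significant".

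**The concern.** The hypothesis and the adequacy analysis refer to different points in time. The hypothesis concerns the end of a two-week interval after one dose. The analysis names the start of that interval and a steady state that belongs to repeated dosing. Day 14 is the sample that bears most directly on the claim, yet the section that judges adequacy does not mention it.

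The paired test does not fill the gap. It asks whether the two routes differ. Two routes that both fall short at day 14, and two that both succeed, can give the same p-value.

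A report that followed section IV.F literally could show high target attainment from first-day exposure and be read as support for two weeks of cover. The time point, fluid and attainment level behind any two-week statement would then be chosen after the data of 10 patients had been seen.

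**Working it through.** **The plan's own figures.**
- *Washout.* Section IV.D says 45 days exceeds five half-lives. With the half-life of about 8.5 days from section II, 45 / 8.5 = 5.3. This reproduces.
- *Detectable difference.* Section IV.F gives 1527 mg·hr/L for AUC between routes, with n = 10 and 80% power. No SD of the paired differences is given, so the figure can only be solved backwards. A two-sided paired t-test at 0.05 needs a standardised difference of 0.996, which implies an SD of 1527 / 0.996 ≈ 1533. It is neither confirmed nor refuted, and it concerns the difference between routes, not adequacy.

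**Is steady state reached?** Assume mono-exponential decline with k = ln 2 / 8.5 per day.
- Fraction left after 45 days: exp(−45k) = 2.5%. If the 45 days are counted from the day-14 visit, the gap between doses is 59 days and exp(−59k) = 0.8%.
- Accumulation factor at 45 days: 1 / (1 − 0.025) ≈ 1.03.

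The second dose is in effect another first dose. Each period is a single-dose profile.

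**Can the initial level stand in for two weeks?**
- Day-14 level relative to the initial level: exp(−14k) = 0.32. For assumed half-lives from 6 to 14 days, the range is 0.20 to 0.50.
- Share of the 0-14 day AUC that falls in the first 12 hours: (1 − exp(−0.5k)) / (1 − exp(−14k)) = 0.040 / 0.681 = 5.9%. The range is 7.0% to 4.9% for half-lives of 6 to 14 days.

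The simulation inputs therefore describe about one-seventeenth of the exposure the hypothesis refers to. A multi-compartment profile, or slow uptake after intraperitoneal dosing, would change these percentages. It would not turn a 12-hour quantity into a 14-day one.

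**Does the attainment level matter with 10 patients?** This is an illustration only, for one route and one fluid. Assume log-normal day-14 concentrations and estimate attainment as Φ(mean / SD) of the log concentration relative to the target. The chance that the estimate reaches a given level is:

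| True attainment | estimate ≥80% | estimate ≥90% | estimate ≥95% |
|---|---|---|---|
| 80% | 53% | 18% | 6% |
| 90% | 89% | 54% | 27% |

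If raw counts are used, 10 of 10 above target gives an exact one-sided 95% lower bound of 0.05^(1/10) = 74%.

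**The case against.** **The study is descriptive.** Section IV.C says so, and the primary endpoints in section IV.A are to determine pharmacokinetics. Section IV.G claims only that the results may allow further applications. A profile of attainment across MIC values can be useful without a pass/fail verdict. This stands, and it limits how serious the point is. It does not explain why the profile would be computed at the wrong time points for the stated hypothesis.

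**Steady state may be a modelled quantity.** The Pharmacokinetic analysis text plans a population model to examine other dosing strategies, and uses non-steady-state equations for volume. That reading is possible, but section IV.F never links the adequacy analysis to that model, and the hypothesis is about a single dose.

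**The target may be in the missing figures.** This stands. A reader might infer that the plan has no PK/PD target at all, but the documents as read do not support that. Section IV.D does name the index in its passage on resistance ("we will maximize the minimum inhibitory concentration to area under the curve ratio"), without a value. What can be said is that no readable sentence gives a target value, an attainment level or a day-14 criterion.

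**The data are there.** A reader might infer that the trial cannot decide its own hypothesis. That goes too far. Plasma and peritoneal fluid are taken on days 7 and 14 by both routes, and Cmin is to be calculated in both fluids. The fault lies in the analysis as specified, not in the design or the sampling.

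**Conclusion.** The point holds as a mismatch between hypothesis and analysis. The adequacy analysis as written does not test the two-week claim. One of its two named points, steady state, does not occur in a single-dose period (about 2.5% left at 45 days). The other, the initial level, is about three times the day-14 level. The simulation inputs cover about 6% of the 14-day exposure. These sizes rest on the plan's half-life of about 8.5 days and on mono-exponential decline.

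It would be wrong to say that adequacy is judged only at steady state, because the plan names the initial concentration as well. The unstated attainment level is a secondary gap: it is missing detail rather than a wrong rule, and the table above shows only that with 10 patients the choice affects the answer. The change should be made before samples are assayed. It does not call the design into question.

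**What to change.** 1. In section IV.F, Analysis of pharmacodynamic targets, replace the initial and steady-state wording with: initial and day-14 (end of the two-week interval after a single dose).
2. Compute the probability of target attainment from day-14 concentrations, or from exposure over 0-14 days, in both plasma and peritoneal fluid and for each route. Add these quantities to the simulation inputs. If only the time-point wording changes, a day-14 attainment cannot be computed from Cmax and AUC0-12.
3. If steady state under a simulated repeat regimen is also of interest, label it as a separate model-based exploration.
4. Before assay, state the PK/PD target, unless the figures not shown already give it, and the attainment level that will be treated as adequate. The choice of level is the sponsor's. Report attainment with its confidence bound. The bound will be wide: under the log-normal model above, a one-sided 95% lower bound reaches 90% in about 15% of trials when true attainment is 95%, and in about 53% when it is 99%.
5. State that the paired t-test describes the difference between routes and does not decide adequacy.

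**Cost.** A few sentences of plan text and a revised simulation, with no extra patients, visits or samples. The downside is that the sponsor may have to report that a route or fluid falls short at day 14, or that 10 patients leave the question undecided.

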### **II. Background and Significance:**

Every year in the United States approximately 110,000-115,000 patients are newly diagnosed with end-stage renal disease (ESRD) and begin treatment with renal replacement therapy. Nearly 10,000 of these patients are started on peritoneal dialysis (PD). The use of home dialysis has increased significantly (35% increase) in the last decade, with 95% of home dialysis patients undergoing PD. Infectious peritonitis is a leading major morbidity associated with PD, and it accounts for approximately 18% of infection-related mortality in PD patients. Severe or prolonged peritonitis can lead to peritoneal membrane failure, ultimately causing technical failure of PD and requiring transition to traditional hemodialysis methodologies. Rapid and effective treatment of peritonitis is required to reduce inflammation and preserve peritoneal membrane function. The current standard of care involves empiric antibiotics covering gram positive organisms as staphylococcus aureus, coagulase negative staphylococcus and enterococcus are common infecting pathogens. Vancomycin is commonly employed at most institutions as there is a risk of MRSA infections in this patient population. Addition of a second drug for gram negative bacteria coverage is recommended until culture and sensitivity results are available. Intravenous or intraperitoneal administration of antibiotics can be utilized; however, guidelines recommend the intraperitoneal administration of antibiotics with a dwell time of at least 6 hours because it provides instant, high, and sustained concentrations of the antibiotic in the peritoneal fluid. Although vancomycin covers the majority of gram positive organisms that cause peritonitis, its use can be cumbersome in PD patients. Plasma vancomycin drug concentration monitoring must occur to evaluate for vancomycin accumulation. Additionally, vancomycin must be re-administered every 3-5 days in order to maintain steady-state trough concentrations around 15 mcg/ml. Similarly to vancomycin, dalbavancin interferes with cell wall synthesis. This is done through binding of the D-alanyl-D-alanine terminus of the cell wall peptidoglycan. Dalbavancin has been shown to rapidly reach therapeutic systemic concentrations and to have an extended half-life of ~8.5 days. Dalbavancin has been shown safe and effective with a treatment doses of 1500 mg once or 1000 mg followed by a 500 mg dose on day 7. Dalbavancin pharmacokinetics were evaluated in patients who had hepatic or renal impairment. This study showed compared to healthy subjects dalbavancin exposure was not increased in mild renal impairment, exposure was ~50% higher in moderate renal impairment, 100% higher in severe renal impairment, and not significantly different in end stage renal disease

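### In the readable text, the only MIC-based analysis names Cmax and AUC0-12 as its exposure inputs; for plasma these hardly respond to day-14 exposure, so a late metric should be added to test the 2-week hypothesis

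*Combined protocol and SAP*

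**What the plan says.** The Hypothesis in section I reads "Dalbavancin maintains adequate plasma and peritoneal fluid concentrations for 2 weeks after a single 1500 mg dose", by either route. Adequacy therefore has a 2-week horizon and covers two fluids.

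Section IV.C schedules intensive sampling on day 0, and then "Patients will report for a single PK measurement on study days 7 and 14". The intraperitoneal dose is "administered in the peritoneal dialysis fluid with a 6 hour dwell time". Section IV.F, Pharmacokinetic analysis, lists Cmax, Cmin, the elimination rate constant, half-life, AUC0-∞ and AUC0-12, among others. It also plans a NONMEM or ADAPT II model to "examine the effects of varying dosing strategies on plasma and peritoneal fluid concentrations". No MIC or target is mentioned there.

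MICs enter under Analysis of pharmacodynamic targets in the same section. The aim is to judge whether initial and steady-state concentrations in plasma and peritoneal fluid are adequate against common pathogens. The method is a Monte Carlo PTA: "The model randomly applies values for $C_{max}$ and $AUC_{0-12}$ derived from data obtained from the study patients". The next sentences bring in CLSI and EUCAST MIC distributions and compare them with plasma concentrations; peritoneal fluid is not named at that step. PTA is then compared between routes by paired t-test.

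Outside the analysis plan, the section on drug-resistant bacteria says the dosing strategy will "maximize the minimum inhibitory concentration to area under the curve ratio". It gives no time window and describes no analysis.

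**The concern.** The question concerns the end of a 14-day interval, but the named PTA inputs describe its first 12 hours. For a drug said "to have an extended half-life of ~8.5 days", two patients could have nearly the same Cmax and AUC0-12 and very different concentrations on day 14. A high PTA on these inputs would then not support adequacy for 2 weeks, and a low one would not refute it.

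Two features add to this. The PTA's purpose mentions steady state, although each period has a single dose, so no late time point is fixed. And where MICs are compared with exposure, only plasma is named, although the hypothesis includes peritoneal fluid. Day-7 and day-14 concentrations will be available, but no readable sentence says how they will be judged against MICs. That judgement could then be made after the data are seen.

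**Working it through.** **Plan's own figure.** The PTA section states no numerical result. The one stated figure built on the half-life is the washout, 45 days or more, said to exceed 5 half-lives: 5 × 8.5 = 42.5 days, below 45, so it reproduces.

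**Inputs.** Half-life of about 8.5 days = 204 h (Background). Horizon 14 days = 336 h (Hypothesis). Dwell 6 h (section IV.C). The half-lives of 4.25 days (102 h) and 17 days (408 h) are assumptions: half and double the stated value.

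**Plasma, simple decline from C0 (intravenous type).** With k = ln 2 / half-life:
- AUC0-12 / C0 = (1 − exp(−12k)) / k
- AUC0-14d / C0 = (1 − exp(−336k)) / k
- C(day 14) / C0 = exp(−336k)

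| Half-life | k (per h) | AUC0-12/C0 (h) | AUC0-14d/C0 (h) | C(day 14)/C0 |
|---|---|---|---|---|
| 102 h | 0.00680 | 11.52 | 132.15 | 0.102 |
| 204 h | 0.00340 | 11.76 | 200.34 | 0.319 |
| 408 h | 0.00170 | 11.88 | 256.02 | 0.565 |
| Ratio, 408 h to 102 h | | 1.031 | 1.937 | 5.54 |

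At 204 h, AUC0-12 is 11.76 / 200.34 = 5.9% of AUC0-14d. Cmax equals C0 here and carries no half-life information.

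**Two-phase decline (assumed).** C(t)/C0 = f·exp(−at) + (1 − f)·exp(−kt), with f = 0.3, 0.5 or 0.7 and a fast half-life of 6, 12 or 24 h. At a slow half-life of 204 h, AUC0-12 is 7-13% of AUC0-14d. For a slow half-life of 408 h against 102 h, AUC0-12 changes by 1.0-2.5%, AUC0-14d by 1.6- to 1.9-fold and day-14 concentration 5.5-fold.

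**Plasma after intraperitoneal dosing (assumed).** First-order absorption during the 6 h dwell only, absorption half-life 2-12 h, one compartment: C(t) is proportional to ka/(ka − k)·(exp(−kt) − exp(−ka·t)) up to 6 h, then declines as exp(−k(t − 6)). At 204 h, AUC0-12 is 4.5-4.9% of AUC0-14d. From 102 h to 408 h, AUC0-12 changes by 2.4-2.6%, Cmax by 1.6-2.0%, AUC0-14d 1.9-fold and day-14 concentration 5.5-fold.

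**Where the argument stops.** AUC0-12 does respond to half-lives of hours: it is 6.49, 8.66 and 10.14 × C0 at 6, 12 and 24 h, against 11.76 × C0 at 204 h. Peritoneal fluid was not quantified for either route. After intraperitoneal dosing, its early concentrations reflect the instilled dose and the dwell, so the plasma figures do not carry over.

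**The case against.** The strongest objection is that two figures in the pharmacodynamic part of section IV.F are not shown. They may define targets, exposure metrics or a time window. This stands: the point covers the readable text only, and a reader should not infer that the plan has no target or no rule for late concentrations.

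Second, the plan has late-time content: day-7 and day-14 samples, Cmin, half-life, AUC0-∞ and a model of both fluids. The phrase about comparing MICs with plasma concentrations is not expressly confined to Cmax and AUC0-12. So a reader might infer that the trial cannot test its 2-week hypothesis at all, and the documents do not support that; the data will exist. Still, no readable sentence links Cmin, day 7 or day 14 to an MIC, so the gap in the MIC analysis remains.

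Third, aims and primary endpoints are descriptive pharmacokinetics, and PTA is not a listed endpoint. This stands and limits the stakes.

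Fourth, the calculation shows ratios of exposure, not a change in PTA. This also stands: without a stated target, no PTA can be computed, and it cannot be said that the reported PTA would be too high or too low.

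Finally, a reader might infer that Cmax and AUC0-12 are wrong and should go. They are reasonable for early exposure, which is part of the stated purpose; the defect is that nothing late stands beside them.

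**Conclusion.** The point holds, as something that should be fixed, with medium confidence. In the readable text, the named PTA inputs omit any day-7 or day-14 metric, and the MIC comparison names plasma only, while the hypothesis is adequacy in both fluids for 2 weeks. For plasma, over half-lives of 4.25 to 17 days, AUC0-12 moves by about 3% or less while day-14 concentration moves about 5.5-fold. The PTA as written would therefore not test the 2-week claim.

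This rests on the stated half-life of about 8.5 days, the assumed range around it, and the assumed two-phase and absorption profiles. Nothing is shown numerically for peritoneal fluid. It is a gap in one analysis, not in sampling or in the primary endpoints.

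**What to change.** In Analysis of pharmacodynamic targets (section IV.F):
- Add day-14 concentration relative to MIC as a PTA input, taken from the measured day-14 samples, with variability simulated from the NONMEM or ADAPT II model already planned.
- Add model-based AUC over days 0-14 relative to MIC as a supporting metric. It cannot replace the day-14 metric, because it averages over the interval and moves only 1.6- to 1.9-fold where day-14 concentration moves 5.5-fold.
- Do both for plasma and peritoneal fluid and for each route, and name both fluids in the MIC-comparison sentence.
- Set the targets before analysis.
- Keep Cmax and AUC0-12 for early exposure, and base the 2-week conclusion on the late metric.
- If the figures not shown already define such metrics, make the text agree with them.

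The cost is wording and modest extra simulation, with no new samples, visits or patients. The downside is that plasma AUC0-14d depends on the model, because no plasma sample falls between the day-0 exchange and day 7. The "linear trapezoidal method" planned for other AUCs would not serve here: at a half-life of 8.5 days, applied to the planned plasma times, it would overstate AUC0-14d by about 2.5% under simple decline and by 8-46% in the assumed two-phase profiles. That error is a cost of the added metric, not a fault of the PTA as written.
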